6.5 IMP Accountability

IMP accountability is documented in the IRT by the unblinded clinical research associate (CRA).

The investigator and the pharmacist must agree to only dispense IMP to patients enrolled in the study. The unblinded pharmacist must maintain an adequate record of the receipt and distribution of the IMP. This record must be available for inspection by the unblinded CRA at any time.

6.6 Unblinding Procedures

Global Patient Safety, H. Lundbeck A/S, the investigator or the pharmacist (if applicable) and the DMC will have access to the unblinded information for the double-blind treatment for each patient. Access to these details will be via IRT.

The IRT unblinding procedure is described in the *IRT User Guide*.

The investigator may only break the code for a patient if knowledge of the IMP is necessary to provide optimal treatment to the patient in an emergency situation. If possible, the investigator must consult the CRA (in some cases it may be the medical monitor) before breaking the code. The investigator must record the date and reason for breaking the code on the *IMP Code Break Form*. If the emergency situation was an adverse event, it must be recorded on an *Adverse Event Form*. The CRA (in some cases it may be the medical monitor) must be notified immediately. The IRT will capture the date and time of the code break call. Information on the allocated treatment will be provided during the call and by fax or email, depending on availability/preference. When the code is broken for a patient, the patient must be immediately withdrawn from the study. If this occurs during a visit, the investigator must complete the visit as a *Withdrawal Visit*; otherwise, the patient will be asked to have a *Withdrawal Visit*.

6.7 Post-study Access to IMP(s)

Patients in the study will have access to appropriate medical care after they complete or withdraw from the study.

7 Concomitant Medication

Concomitant medication is any medication other than the IMP that is taken during the study up until the Safety Follow-up Visit, including during the screening period.

The concomitant medications that are disallowed or allowed with restrictions during the study are summarized in [Appendix II](#).

Details of all concomitant medication (prescription and over the counter), herbal remedies, non-pharmacological interventions, vitamin and mineral supplements for the treatment of migraine taken and substance use <3 months prior to the Screening Visit must be recorded in the electronic case report form (eCRF) at the first visit. Any changes (including reason for changes) in concomitant medication and non-pharmacological interventions must be recorded at each subsequent visit. Any changes in substance use must be collected at selected visits until the Safety Follow-up/Withdrawal Visit.

Vaccinations (including COVID-19 vaccines) are allowed provided the vaccinations have been completed for at least 14 days prior to the Screening Visit. Vaccinations during the study are allowed providing the vaccination is received at least 3 days after the IMP administration. The vaccinations, including brand names, if used during the study must be reported as concomitant medications.

Details of all migraine preventive treatment failure medications (prescription and over-the-counter) taken within 10 years prior to the Screening Visit must be recorded in the eCRF at the Screening Visit.

For any concomitant medication for which the dose was increased due to worsening of a concurrent disorder after enrolment in the study, the worsening of the disorder must be recorded as an adverse event.

For any concomitant medication initiated due to a new disorder after enrolment in the study, the disorder must be recorded as an adverse event.

8 Study Visit Plan

8.1 Overview

An overview of the procedures and assessments to be conducted during the study and their timing is presented in [Panel 2](#). Further details are in chapter [9](#).

Appropriate risk assessment and mitigations will be done in case of restrictions due to COVID-19, which will be described in detail in a separate COVID-19 mitigation plan.

The Screening Visit (Visit 1) is performed 28 to 30 days before the Baseline Visit (Visit 2). At the Baseline Visit (Visit 2), the IMP is administered. The Primary Outcome Visit (Visit 4)

is performed 4 weeks after the Baseline Visit. A Safety Follow-up Visit (Visit 6) is performed 8 weeks after the Primary Outcome Visit.

At the visits, all assessments may be completed over a maximum of 2 consecutive days (with the exception of PROs - see paragraph below); if so, the first day is considered the “visit” day according to the schedule.

If the date of a visit does not conform to the schedule, subsequent visits should be planned to maintain the visit schedule relative to the Baseline Visit.

Patients will record eDiary headache data on a daily basis from the Screening Visit until the Safety Follow-up Visit or Efficacy Follow-up/Withdrawal Visit. At each visit, a compliance check of eDiary (based on eDiary reporting) will be conducted. Additionally, ongoing evaluation of eDiary compliance will be performed by the site and more frequent contact with patients may be needed in case of non-compliance. See section 9.2.1.2 for further details on eDiary.

Patients will complete the PROs in alignment with scheduled visit dates. PROs scheduled at the Baseline Visit (Visit 2) must be completed in the clinic at the visit date and before the infusion. PROs scheduled in alignment with all other visits can be completed on the day or within 3 days prior to the scheduled visit date. See section 9.2.1 for further details on PROs.

Patients who withdraw prior to the Primary Outcome Visit (Week 4), except for those who withdraw their consent, will have a Withdrawal Visit as soon as possible, an Efficacy Follow-up (Phone Contact) Visit at Week 4, and a further Safety Follow-up Visit at 12 weeks after administration of the IMP (the Baseline Visit). If the Withdrawal Visit takes place at Week 4, an Efficacy Follow-up (Phone Contact) Visit at Week 4 is not required (see section 8.10).

Visit 3, Visit 4 (Primary Outcome Visit), Visit 5, and Withdrawal Visit can be conducted as a clinic visit to the site by the patient or can be provided as a home visit by a healthcare provider/study site staff with or without a televisit through teleconferencing. Before these visits are conducted, patients will have the option to choose the types of visits to be conducted and these are allowed to be changed during the study. The type of visits conducted must be recorded in the eCRF. Further information on the type of visits will be provided in the *Site Guide for Off-Site Nursing Services and TeleVisit Solutions Site Reference Guide*.

After completing or withdrawing from the study, the patient must be treated in accordance with usual clinical practice.

8.2 Screening Visit (Visit 1)

The Screening Visit must be conducted as a visit to the site. Signed informed consent must be in place before any study-related assessments are performed (including collection of relevant documentation from the patient’s treating physician) and may be obtained prior to the Screening Visit. See section 9.1 for further details on screening assessments and chapter 12 for further details on relevant documentation from the treating physician.

CCI

At the Screening Visit, the patient must be assisted with the provisioning of the eDiary and PROs and must be trained in their use and compliance requirements. Details will be provided in a separate *eDiary and PRO site information guide* (see section 9.2.1.2 for further details on the eDiary and section 9.2.1 for further details on PROs).

In exceptional cases, the screening period (the visit interval between the Screening and Baseline Visits) may be extended with approval from the sponsor provided the Lundbeck medical expert (or the CRO's medical monitor) accepts the rationale provided for the extension.

Prior to the Baseline Visit, study-specific eligibility must be reviewed by the CRO's medical monitor to advise if the patient appears eligible or not according to the selection criteria of the protocol.

8.2.1 Pre-screening

Each site must record in a pre-screening log which patients attended the Screening Visit.

8.2.2 Patient Identification Card

Each patient will be provided with a patient identification card that states, at a minimum, the name of the IMP, the study number, the patient identification number, the investigator's name, and an emergency telephone number providing 24-hour service.

The patient identification card should be returned to the investigator upon completion of the patient's participation in the study.

8.2.3 Re-screening

Re-screening is only allowed for patients with a *complete* Screening Visit and who do not fulfil the following:

- The required duration of a washout period for a medication that is disallowed prior to screening, or
- A stable usage period for a medication that is allowed with restrictions prior to screening.

Rescreening may also be allowed for patients with a *complete* Screening Visit but are required to be in quarantine due to a positive COVID-19 test or other reasons due to COVID-19.

The patient must already have either started the washout prior to screening or be on the allowed dosage as part of their standard clinical care. Washout or change in dosage may not be done specifically for inclusion into this study.

Authorization for re-screening may only be granted by the sponsor's medical expert (or the CRO's medical monitor) after a thorough review of all data from the original Screening Visit.

The new Screening Visit must be conducted as a visit to the site. At the new Screening Visit, the patient must sign a new *Informed Consent Form*. At the new Screening Visit, the patient will be assigned a new screening number. A re-screened patient must have a *completely* new Screening Visit, and all the eligibility criteria must be re-assessed at the new Screening Visit.

The following information will be recorded in the eCRF at the new Screening Visit:

- that the patient has previously been screened for the study
- that re-screening has been authorized by the sponsor's medical expert (or the CRO's medical monitor)
- the screening number that was assigned to the patient at the original Screening Visit

If a patient is re-screened, no assessment data from the original Screening Visit will be used.

A patient may only be re-screened once.

8.3 Baseline + IMP Visit (Visit 2)

The Baseline Visit must be conducted as a visit to the site and will occur 28 to 30 days after the Screening Visit. In exceptional cases, the visit interval between the Screening and Baseline Visits may be extended with consent from the Lundbeck medical expert, provided the Lundbeck medical expert accepts the rationale provided for the extension.

Prior to the Baseline Visit, study-specific eligibility must be reviewed by the CRO's medical monitor to advise if the patient appears eligible or not according to the selection criteria of the protocol.

At the Baseline Visit, inclusion and exclusion criteria review must be done prior to dosing (see section 5.3 for further details on selection criteria). A compliance check of the eDiary, based on the 28-day screening period, will be conducted and the patient must be assisted with re-training if necessary.

On the Baseline Visit day, patients must ensure to complete the eDiary recording of headaches that ended prior to infusion (i.e., for headaches which are ongoing or not yet recorded in the eDiary). See section 9.2.1.2 for further details on the eDiary.

PROs which are scheduled in alignment with the Baseline Visit must be completed in the clinic and prior to infusion. CCI

It is preferable that the same order of assessments is used per patient and if the scheduled time of the day for the assessments is as consistent as possible across all the study visits. Clinician-reported outcomes (ClinROs; CCI and C-SSRS) must be administered by the authorized rater after the PROs are completed and prior to infusion. See section 9.2.1 for further details on PROs.

At the Baseline Visit, the patients will receive a dose of IMP. See section 6.2 and *Infusion Guidelines* for further instructions on procedures associated with administering the IV IMP.

Prior to IMP infusion:

- Patients must complete the PROs. PROs can be completed at the patient's convenience before or after the pre-infusion blood and urine sampling.
- The following assessments must be conducted/collected: vital signs (including blood pressure, pulse, respiratory rate, and body temperature), concomitant medications and substances (prescription and non-prescription), non-pharmacological interventions, adverse events, physical and neurological examinations, ECG, blood sampling (for clinical safety laboratory tests, CCI [REDACTED] ADA including NAb, and optional CCI [REDACTED] and urine sampling (for clinical safety laboratory and pregnancy tests), CCI [REDACTED] and C-SSRS. Vital signs must be assessed prior to blood sampling.

During IMP infusion: Infusion-related reactions (IRRs) must be checked as part of the overall adverse event collection. IRRs must be assessed after the adverse event collection.

After end-of-IMP-infusion and before the patient is discharged from the site:

- Patients must be monitored for at least 2 hours.
- The following assessments must be conducted: vital signs (including blood pressure, pulse, respiratory rate, and body temperature), IRRs, and adverse events. IRRs must be assessed after the adverse event collection.
- A blood sample for CCI [REDACTED] quantification must be taken immediately after end of infusion (EOI) and 2 hours after EOI. Vital signs must be assessed prior to blood sampling.
- Patients will be requested to stay longer should the investigator or designee determine this is clinically warranted.
- After the infusion, the patients will be under observation, but not confined to bed, unless the investigator or designee decides, based on the patient's condition, that it is in the best interest of the patient to be confined to bed.

8.4 Visit 3

The Week 2 Visit can be conducted as a visit to the site or a home visit with or without a televisit. See section 8.1 for further details on the types of visits. The Week 2 Visit should be planned to maintain the visit schedule relative to the Baseline Visit.

A compliance check of the eDiary will be conducted. See section 9.2.1.2 for further details on the eDiary.

PROs which are scheduled in alignment with the scheduled visit can be completed on the day or within 3 days prior to the scheduled visit date. CCI [REDACTED]

[REDACTED] It is preferable that the same order of assessments is used per patient and if the scheduled time of the day for the assessments is as consistent as possible across all the study visits. It is preferred to take the CCI [REDACTED] in the

morning, if possible. This may put the CCI out of the order in relation to the other assessments when performed in the morning. See section 9.2.1 for further details on PROs.

Blood sampling will be taken for CCI and ADA (including NAb) quantification. Relevant assessments for safety will be conducted including blood and urine sampling for clinical safety laboratory tests and C-SSRS. C-SSRS must be administered by the authorized rater after the PROs are completed. Adverse events, concomitant medication (prescription and non-prescription) and non-pharmacological interventions will be collected.

8.5 Primary Outcome Visit (Visit 4)

The Primary Outcome Visit can be conducted as a visit to the site or a home visit with or without a televisit. See section 8.1 for further details on the types of visits. The Primary Outcome Visit should be planned to maintain the visit schedule relative to the Baseline Visit.

A compliance check of the eDiary will be conducted. See section 9.2.1.2 for further details on the eDiary.

PROs which are scheduled in alignment with the Primary Outcome Visit can be completed on the day or within 3 days prior to the scheduled visit date. CCI

It is preferable that the same order of assessments is used per patient and if the scheduled time of the day for the assessments is as consistent as possible across all the study visits. It is preferred to take the CCI in the morning, if possible. This may put the CCI out of the order in relation to the other assessments when performed in the morning. See section 9.2.1 for further details on PROs. CCI must be administered by the authorized rater after the PROs are completed. Adverse events, concomitant medication (prescription and non-prescription), and non-pharmacological interventions will be collected.

Blood sampling will be taken for CCI ADA (including NAb), and optional CCI. Relevant assessments for safety will be conducted including blood and urine sampling for clinical safety laboratory tests, pregnancy test, and C-SSRS. C-SSRS must be administered by the authorized rater after the PROs are completed.

8.6 Visit 5

The Week 8 Visit can be conducted as a visit to the site or a home visit with or without a televisit. See section 8.1 for further details on the types of visits. The Week 8 Visit should be planned to maintain the visit schedule relative to the Baseline Visit.

A compliance check of the eDiary will be conducted. See section 9.2.1.2 for further details on the eDiary.

PROs which are scheduled in alignment with the scheduled visit can be completed on the day or within 3 days prior to the scheduled visit. CCI

It is preferable that the same order of assessments is used per patient and if the scheduled time of the day for the assessments is as consistent as possible across all the study visits. It is preferred to take the [CCI] in the morning, if possible. This may put the [CCI] out of the order in relation to the other assessments when performed in the morning. See section 9.2.1 for further details on PROs. [CCI] must be administered by the authorized rater after the PROs are completed. Adverse events, concomitant medication (prescription and non-prescription), and non-pharmacological interventions will be collected.

Blood sampling will be taken for [CCI] and ADA (including NAb) quantification. Relevant assessments for safety will be conducted including blood and urine sampling for clinical safety laboratory tests and C-SSRS. C-SSRS must be administered by the authorized rater after the PROs are completed.

8.7 Safety Follow-up Visit (Visit 6)

Patients will attend the Safety Follow-up Visit which must be conducted 8 weeks after the Primary Outcome Visit (i.e., 12 weeks after administration of IMP). The Safety Follow-up Visit must be conducted as a visit to the site. A safety follow-up is conducted to capture adverse events that occur during the safety follow-up period as well as to follow up on the outcome of adverse events ongoing at the end of the treatment period. Relevant assessments for safety will be conducted including blood and urine sampling for clinical safety laboratory tests, pregnancy test, and C-SSRS. C-SSRS must be administered by the authorized rater after the PROs are completed. Adverse events, concomitant medication (prescription and non-prescription), and non-pharmacological interventions will be collected.

The eDiary closeout will take place at the Safety Follow-up Visit while the patient is at the site. Details will be provided in a separate *eDiary and PRO training material*. See section 9.2.1.2 for further details on the eDiary.

PROs which are scheduled in alignment with the scheduled on-site visit can be completed on the day or within 3 days prior to the scheduled on-site visit. [CCI]

[CCI] It is preferable that the same order of assessments is used per patient and if the scheduled time of the day for the assessments is as consistent as possible across all the study visits. It is preferred to take the [CCI] in the morning, if possible. This may put the [CCI] out of the order in relation to the other assessments when performed in the morning. See section 9.2.1 for further details on PROs. [CCI] must be administered by the authorized rater after the PROs are completed.

Blood sampling will be taken for [CCI] and ADA (including NAb) quantification.

A proportion of patients who complete the Safety Follow-up Visit (Week 12) will be asked to provide additional blood samples for post-study immunogenicity testing at 12-week intervals (potentially up to 12 months relative to the infusion date). The number of patients from

whom these samples will be collected will be decided during the study in consultation with the sponsor.

For patients with a clinically significant out-of-range clinical safety laboratory test value at the Safety Follow-up Visit, further safety follow-up should be scheduled in accordance with usual clinical practice until the value normalizes or stabilizes or a diagnosis or reasonable explanation has been established. Any further safety follow-up after the last protocol-specified contact with the patient will be recorded in the patient's medical records and not in the eCRF; see section 10.5 for details.

For adverse events that were ongoing at the end of the treatment period and that resolved during the safety follow-up period, the stop date must be recorded.

For non-serious adverse events still ongoing at the Safety Follow-up Visit, the *Ongoing Adverse Event* checkbox on the *Adverse Event Form* must be ticked. SAEs must be followed until resolution or the outcome is known.

Patients who withdraw from the study prior to the Primary Outcome Visit, except for those who withdraw their consent, will have a Withdrawal Visit as soon as possible and a further Safety Follow-up Visit at 12 weeks after administration of IMP (the Baseline Visit). At the Safety Follow-up Visit, withdrawn patients will not be required to complete the efficacy assessments. Details will be provided in a separate *eDiary* and *PRO training material*.

The safety follow-up for patients who withdraw consent must be performed, if at all possible; any information collected will be recorded in the patients' medical records.

CCI

8.8 Unscheduled Visit

An unscheduled visit may occur throughout this study if needed preferably as a site visit (depending on the assessments required). At these visits, clinical safety laboratory tests, ECG, vital signs, physical or neurological examinations can be performed. In case of any additional tests performed that are not covered by the existing tests specified in the protocol and the eCRF, the results can be reported in connection with an AE reporting (see chapter 10) or documented in the medical notes, as applicable. Adverse events, concomitant medication (prescription and non-prescription), and non-pharmacological interventions will be collected.

8.9 Withdrawal Visit

Patients who withdraw from the study prior to the Primary Outcome Visit (Week 4) will have a Withdrawal Visit, if possible, which can be conducted as a visit to the site or a home visit with or without a televisit. The visit must be scheduled as soon as possible after withdrawal.

At the Withdrawal Visit, a compliance check of the eDiary will be conducted. The eDiary assessments should continue on a daily basis until Week 4. Thus, if the patient withdraws between Week 3 and Week 4, then the Withdrawal Visit should be scheduled at Week 4 to align with the eDiary closeout. If the Withdrawal Visit takes place during the treatment period and prior to Week 3, then the eDiary assessments should continue on a daily basis until Week 4 and the patient will be contacted via telephone for an Efficacy Follow-up Visit (phone contact) at Week 4 for the eDiary closeout (see section 8.10). Details will be provided in a separate *eDiary and PRO training material*. See section 9.2.1.2 for further details on the eDiary.

PROs which are scheduled in alignment with the Withdrawal Visit can be completed on the day or within 3 days prior to the scheduled visit date. CCI

It is preferable that the same order of assessments is used per patient and if the scheduled time of the day for the assessments is as consistent as possible across all the study visits. It is preferred to take the CCI in the morning, if possible. This may put the CCI out of the order in relation to the other assessments when performed in the morning. See section 9.2.1 for further details on PROs. CCI must be administered by the authorized rater after the PROs are completed.

Blood sampling will be taken for CCI and ADA (including NAb) quantification, and optional CCI. Relevant assessments for safety will be conducted including blood and urine sampling for clinical safety laboratory tests and C-SSRS. C-SSRS must be administered by the authorized rater after the PROs are completed. Adverse events, concomitant medication (prescription and non-prescription), and non-pharmacological interventions will be collected.

No new information will be collected from patients who withdraw from the study, except information collected in relation to the scheduled Withdrawal Visit or needed for the follow-up of adverse events (section 10.5).

The reason for withdrawal must be recorded in the eCRF.

For a patient who withdraws consent:

- If the patient withdraws consent during a visit and then agrees to it being the final visit, the investigator will complete the visit as a Withdrawal Visit and all the data collected up to and including that visit will be used.
- If the patient withdraws consent during a telephone conversation, the investigator will ask the patient if he or she will attend a Withdrawal Visit. If the patient:
 - Agrees to attend a Withdrawal Visit, all the data collected up to and including that visit will be used
 - Refuses to attend a Withdrawal Visit, the investigator should attempt to follow the patient's safety and future treatment; any information collected will only be recorded in the patient's medical records
- If the patient explicitly requests that the patient's data collected from the time of withdrawal of consent onwards not be used, this will be respected.

The withdrawal visit does not apply if a patient withdraws during the safety follow-up period (for whatever reason). Then the investigator should attempt to follow the patient's safety and future treatment; any information collected will only be recorded in the patient's medical records.

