The total study duration from the Screening Visit to the Safety Follow-up Visit is approximately 16 weeks and includes a screening period (28 to 30 days), treatment period (4 weeks), and safety follow-up period (8 weeks). Patients will complete a daily headache eDiary from the Screening Visit until the Safety Follow-up Visit or Efficacy Follow-up/Withdrawal Visit.

Patients will receive the IMP in the form of a single-dose administration at the Baseline Visit with either Lu AG09222 or placebo by IV infusion over 30 minutes (+15 minutes).

During the Baseline Visit, assessments of safety will be performed before and after the infusion. The PROs must be completed prior to infusion. Patients must complete the eDiary recording of headaches that ended prior to infusion (i.e., for headaches which are ongoing or not yet recorded in the eDiary).

Patients who withdraw prior to the Primary Outcome Visit (Week 4), except for those who withdraw their consent, will have a Withdrawal Visit as soon as possible, an Efficacy Follow-up (Phone Contact) Visit at Week 4, and a further Safety Follow-up Visit at 12 weeks after administration of the IMP (the Baseline Visit). If the Withdrawal Visit takes place at Week 4, an Efficacy Follow-up (Phone Contact) Visit at Week 4 is not required.

Safety data will be reviewed on an ongoing basis and evaluated regularly by the Lundbeck Safety Committee. In addition, an independent DMC will regularly monitor the safety data according to the *DMC Charter*.

CCI

[Redacted]

CCI

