4.2 Definition of Periods

The trial consists of the following periods:

- Screening Period (28-30 days): Starts at the Screening Visit (Visit 1) and continues up to start of Visit 2 IMP infusion (Week 0).
- Treatment Period (4 weeks): Starts at start of Visit 2 IMP (Week 0) infusion and continues up to and including Visit 4 (Week 4).
- Safety Follow-up Period (12 weeks): Starts at start of Visit 2 IMP (Week 0) infusion and continues up to and including the Safety Follow-up visit (Week 12).

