4.3 Definition of Withdrawal

Participants who have received IMP infusion at Visit 2 and have withdrawn from the trial prior to the Primary Outcome Visit (Week 4), will be described as withdrawn from trial. The complementary group will be described as completed the trial.

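### SAP 4.3 reports patients who withdraw in Weeks 5–12 as completers, and non-serious adverse events learned after they leave may not reach the eCRF

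*Protocol*

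**What the plan says.** **Periods.** Protocol 3.1 sets out a "screening period (28 to 30 days), treatment period (4 weeks), and safety follow-up period (8 weeks"), so safety follow-up there means Weeks 5–12. SAP 4.2 uses the same name for a longer window: "Safety Follow-up Period (12 weeks): Starts at start of Visit 2 IMP (Week 0) infusion". Weeks 5–12 below follows the protocol's meaning.

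**Withdrawal before Week 4.** Protocol 8.7 says: "Patients who withdraw from the study prior to the Primary Outcome Visit, except for those who withdraw their consent, will have a Withdrawal Visit". They also keep a Safety Follow-up Visit 12 weeks after infusion.

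**Withdrawal in Weeks 5–12.** Protocol 8.9 says: "The withdrawal visit does not apply if a patient withdraws during the safety follow-up period (for whatever reason". The investigator should still try to follow the patient's safety, but "any information collected will only be recorded in the patient's medical records".

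**How the SAP labels them.** Under SAP 4.3, treated participants who "have withdrawn from the trial prior to the Primary Outcome Visit (Week 4), will be described as withdrawn from trial". For the rest, "The complementary group will be described as completed the trial". SAP 7.1 and 7.2 use these terms for the disposition table, the reasons for withdrawal and the listing. The Kaplan-Meier plot in 7.2 censors at Visit 4 everyone who finishes the Treatment Period.

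**What the protocol planned.** Section 16.4 has two layers: withdrawals before Week 4 with reasons, and study-level non-completion with reasons, both by treatment group.

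**The concern.** The SAP reports safety over 12 weeks but defines completion at Week 4. A reader of the disposition table would take completion of the trial to mean observation to Week 12. For anyone who left in Weeks 5–12 that is wrong, and nothing visible in SAP section 7 gives the number by arm or the reasons.

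The data rule adds a smaller problem. Adverse-event tables are based on all treated participants (SAP 13.1.1), so a late withdrawal stays in the denominator for the whole 12 weeks. If the investigator later learns of a non-serious event, 8.9 read literally keeps it out of the eCRF and so out of the numerator. Late withdrawal for safety reasons is foreseen: the suicide-risk criterion in Protocol 5.4 applies throughout the study.

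**Working it through.** No figure in the plan needs reproducing; this is a check of definitions and data flow.

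**Step 1: follow one participant who is treated, reaches Week 4 and withdraws at Week 6.**

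| Output or rule | How this participant appears |
|---|---|
| Protocol 16.4, before-Week-4 summary | Not withdrawn |
| Protocol 16.4, study-level summary | Non-completer, with reason |
| SAP 4.3 and 7.1 | Completed the trial |
| SAP 7.2 reasons and listing | Absent |
| SAP 7.2 Kaplan-Meier plot | Censored at Week 4 |
| SAP 13.1.8, adverse events leading to withdrawal | Could appear; no Week 4 limit is stated there |
| SAP 13.1.1, adverse-event denominator | Included |
| SAP 13.2, by-visit laboratory, vital-sign and ECG tables | Not counted where the value is missing |

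The second row is lost between protocol and SAP. Read together, SAP 4.3 and 13.1.8 also allow one person to be both a completer and a withdrawal due to an adverse event.

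**Step 2: set the data rules side by side.**

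- Protocol 8.9, general rule: no new information after withdrawal, except from the scheduled Withdrawal Visit or as needed for adverse-event follow-up under 10.5.
- Protocol 10.5: non-serious events are followed to resolution or the Safety Follow-up Visit, whichever is first. Serious events are followed further and reported to the sponsor. Neither duty excludes late withdrawals.
- Protocol 8.9, late-withdrawal paragraph: medical records only.

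The word *only* in the third rule cannot be squared with the exception in the first or the duties in the second. The same medical-records-only handling applies in 8.9 to a patient who withdraws consent and refuses a final visit. A late withdrawal for any reason is thus handled like a refusal of consent.

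**Step 3: size.** The documents give no late-withdrawal rate. The 5% dropout in Protocol 16.10 is not split at Week 4. The rates below are assumptions.

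- Share of the post-infusion window that the SAP definition of withdrawal does not cover: 8/12 = 67%. This is a length of time, not an amount of data lost.
- Patients mislabelled, taking all 230 as treated: 230 × 0.02 = 4.6, about 5; 230 × 0.05 = 11.5, about 12. At 10% it would be 23.
- In an arm of 92: 92 × 0.02 = 1.8, about 2; 92 × 0.05 = 4.6, about 5.
- Observation time after withdrawal, if departures are uniform over the 8 weeks (4 weeks lost on average): 5 × 4 = 20 to 12 × 4 = 48 patient-weeks, out of 230 × 12 = 2,760. That is 0.7% to 1.7%.

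**The case against.** A reader might infer that all safety information on these patients sits only in medical records and that late losses are invisible in the database. The documents do not support that:

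- The sentence in 8.9 concerns information gathered after withdrawal. Earlier data are collected as usual, including adverse events, laboratory tests and C-SSRS at the Week 8 visit for those still in the study then. An event that causes withdrawal arises before it and belongs on an Adverse Event Form (Protocol 10.3).
- Protocol 8.9 requires the reason for withdrawal in the eCRF, with no Week 4 limit.
- Serious events must still be followed and reported under 10.5.
- SAP 13.1.8 lists adverse events leading to withdrawal, and under SAP 13.2 a late loss shows as a lower n at Week 8 or 12.

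All of this stands. Nor do the documents show that late withdrawers are likelier to have an event, or that 8.7 contradicts 8.9, since the 8.7 paragraph concerns early withdrawals.

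It can also be said that SAP 4.3 is an explicit definition tied to the primary outcome, that nothing visible cancels the 16.4 summary, and that a rationale may lie in SAP section 21, whose text is redacted. The visible headings for section 21 include periods and analysis sets but no change to the withdrawal definition; some headings are redacted too. A rationale cannot be ruled out, but it would not make the label accurate. Protocol 16.7 also planned a summary of days in the study, but SAP section 10 does not visibly repeat it.

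**Conclusion.** The concern holds in a limited form. SAP 4.3 and section 7 report Week 5–12 withdrawals as completers and do not visibly deliver the study-level summary in Protocol 16.4. The late-withdrawal paragraph of Protocol 8.9 conflicts with that section's own exception and with 10.5, so non-serious adverse events learned after a late withdrawal may go unrecorded while the patient stays in the adverse-event denominator.

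At an assumed 2–5% late withdrawal, about 5–12 of 230 patients would be mislabelled and 0.7–1.7% of post-infusion patient-weeks affected. The mislabelling follows from the definition whatever the rate. The loss of events depends on how sites read 8.9 and on whether there is anything to record. The primary endpoint covers Weeks 1–4 and is untouched.

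**What to change.** **SAP 4.3 and 7.** Describe these participants as *completed the Treatment Period, withdrew before Week 12*. Add the Protocol 16.4 summary of study-level completion to Week 12, by arm with reasons. Extend the time-to-withdrawal plot to Week 12.

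**Protocol 8.9.** Reconcile the medical-records-only sentence with the adverse-event exception in the same section and with 10.5, so that the withdrawal date and any adverse-event information obtained up to Week 12 are entered in the eCRF, except after withdrawal of consent. The reason for withdrawal is already required there. Name the period by weeks, because the protocol and SAP define safety follow-up differently.

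**Cost.** One protocol paragraph, one SAP definition, one more disposition summary, a longer plot axis and a little data entry per late withdrawal. No new visit or procedure is needed, since 8.9 already asks the investigator to seek this information.
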